3. STUDY OBJECTIVES

Primary Objective

- To produce preliminary data to design a larger, funded study

Secondary Objectives

- To assess patient comfort in using home telemonitoring for blood pressure combined with pharmacist counseling and monitoring using a survey instrument with a Likert scale
- To assess the ability to collect and monitor hypertension data using Bluetooth enabled mobile health technology
- To determine if blood pressure readings improve with pharmacist interventions

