5. STUDY POPULATION

We are aiming to enroll 20 patient participants for this pilot study. To be eligible for participation, enrollees must be ≥ 18 years old, have a smartphone compatible with the mobile intervention, have been previously diagnosed with hypertension, have uncontrolled hypertension (SBP > 130 mmHg and/or DBP > 80 mmHg), be under the care of a primary care physician in the Family Medicine

Department of the USF Morsani Center for Advanced Care, have had at least one prescription filled at Pharmacy Plus within the last six months, and speak English fluently.

Patients will be excluded if they are already under the care of a clinical pharmacist in the Family Medicine department, are pregnant, or have a serious existing medical condition(s) that may affect their ability to self-monitor their blood pressure (for example, stroke, dementia).

Recruitment

A list of potential patients (Family Medicine patients with diagnosis of hypertension who have had at least one prescription filled at Pharmacy Plus within the last 6 months) will be generated by the Epic support team and identified through the electronic medical records system as well as the pharmacy prescription database. The pharmacists from Pharmacy Plus on this study or 4th year pharmacy students on their Ambulatory Care or Community Pharmacy Rotation will call patients on this list and will discover if the patient meets the final qualification for the study (has a smart phone or other smart device) and is interested in being a part of the study. This is not cold calling, as this list includes eligible patients who have had a prescription filled at Pharmacy Plus within the last 6 months. Each patient on this list has interacted with the pharmacists at Pharmacy Plus when the medication was dispensed. The pharmacists have an established relationship with these patients, as they are involved with the care of these patients. They are involved with the treatment of these patients as they provide pharmacy services when dispensing medications and counseling the patients, as well as some medical services such as vaccine administration.. [name], who practices in the Family Medicine department, is the physician on this study and is aware that these patients will be contacted via phone. We will not be obtaining verbal consent to participate during this phone call.

Enrollment

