6. INTERVENTIONS

Devices

- Smart Phones with Apple Health Software will be used to monitor blood pressure once a day, and results will be sent automatically to the patients EHR (Epic)
- The Omron 10 Series Wireless Upper Arm Blood Pressure Device will be given to the patient to monitor blood pressure at home daily

Pre- and Post-surveys

- A pre- and post-survey will be given at the initial and final in-person appointments, respectively
- These surveys will collect basic patient demographics, knowledge of blood pressure, comfort with checking blood pressure at home, and previous experience working with a pharmacist

Pharmacist Management

- Review of evidence-based therapy and recommendations for improvement if needed
- Educate the patients on how to monitor their blood pressure with their Bluetooth enabled home blood pressure monitor and smart phones

- Patients will be scheduled for a one-hour in-person appointment for the initial study visit where informed consent will be obtained, and for the final study visit
 - At the final study visit, the patients will complete a post-study survey and be given a \$25 gift card upon return of the blood pressure device
- Review results once per week
 - If any patient has an SBP reading > 160 mmHg or DBP > 100 mmHg, they will be instructed to wait five minutes and then recheck their BP. If the BP readings exceed these thresholds for three days in a row, the patients should contact their primary care provider in the clinic for further management.
 - If SBP > 180 mmHg and/or DBP > 120 mmHg, patients will be instructed to call 911 or have someone drive them to the ER immediately
 - There will not be alerts sent to the study pharmacists if the blood pressure readings are above these thresholds
- Follow-up with patients once per week for six (6) weeks via scheduled 20-minute telehealth appointment with each patient via the HIPAA secure and compliant platform, VSee
 - During this telehealth appointment, the study pharmacists will counsel the patients on their blood pressure readings for that week and provide lifestyle education focusing on patient-specific diet and exercise recommendations
- The total duration of the study will be eight (8) weeks

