7. EXPECTED RESULTS

The Hypotheses – It is expected that:

- The study will be able to produce data in order to design a larger, funded study
- Patients will express comfort in using home telemonitoring
- The pharmacists will be able to collect and monitor hypertension data using mobile health technology
- A statistically significant ($p < 0.05$) greater proportion of patients in the after study period will be in proper control of their hypertension ($< 130/80$ mmHg) than in the before study period

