11. DATA MANAGEMENT AND ANALYSIS

- Primary Objective: Preliminary data to design a larger, funded study
 - Captured data and information will be collected in such a way as to make it useful for putting forth a cogent argument for a larger effort.
- BP readings will be captured automatically in Epic
- Mean BP readings will be calculated and compared for the pre- and post-periods, as will the number of patients in and out of blood pressure control
- Pre- and post-study data will be analyzed using a comparison of means (2-tail t-test) and chi-square for comparing low compliant patients (for using the devices) with high compliant patients. The post-study patient satisfaction data will be analyzed using descriptive statistics.

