13. SAFETY MONITORING PLAN

Data Capture

- Survey data will be captured through Qualtrics and then stored in RedCAP
- Blood pressure results will be transmitted through a secure portal within Apple Health from the patient's mobile device to the EHR system, Epic. This process has already been approved and released through USF Health IT.

- The safety of the patient will be our primary concern. All procedures, including patient consent will be carefully performed and double checked by the study coordinator. We will encourage and answer all question from patients.

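### Does the comfort objective lack a matching survey item and a named analysis?

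*Combined protocol and SAP*

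**What the plan says.** - **Objective (Section 3).** One of three secondary objectives is "To assess patient comfort in using home telemonitoring for blood pressure combined with pharmacist counseling and monitoring", measured by a survey with a Likert scale.
- **Hypothesis (Section 7).** "Patients will express comfort in using home telemonitoring". No summary measure, cut-off or test is attached. The p < 0.05 criterion in that section belongs to blood pressure control alone.
- **Survey content (Section 6, Pre- and Post-surveys).** Both surveys cover demographics, knowledge of blood pressure, and "comfort with checking blood pressure at home, and previous experience working with a pharmacist".
- **Timing (Section 6, Pharmacist Management).** "At the final study visit, the patients will complete a post-study survey". The gift card is given there, when the device is returned.
- **Analysis (Section 11).** "Pre- and post-study data will be analyzed using a comparison of means (2-tail t-test") is the general pre/post sentence, which also gives a chi-square for low versus high device compliance. Then comes "The post-study patient satisfaction data will be analyzed using descriptive statistics".
- **Data capture (Section 13).** "Survey data will be captured through Qualtrics and then stored in RedCAP".
- **Size (Section 5).** "We are aiming to enroll 20 patient participants for this pilot study".

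**The concern.** The construct is described in different ways in four places. Section 3 speaks of comfort with the combined service, Section 7 of comfort with telemonitoring, and Section 6 of comfort with taking readings at home. Section 11 speaks of satisfaction. Satisfaction and comfort are not the same: a patient may be pleased with the pharmacist and still find the device or phone link hard to use. Read literally, Section 11 does not say which item or summary answers the comfort objective, or whether the t-test sentence is meant to reach survey scores.

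The post-survey is also tied to an in-person final visit, with no stated handling for those who do not attend. If patients who struggled with the technology were the ones lost, a figure from completers alone would overstate comfort. The pilot exists to supply data for a larger study, so an undefined comfort figure with an unclear denominator would weaken one of its outputs.

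**Working it through.** The documents state no precision, power or attrition figure for this objective, so there is nothing to reproduce. The check is a comparison of the sections, followed by an illustration of what missing surveys could do.

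**1. Is there a matching survey item?** Section 6 lists comfort with checking blood pressure at home in both surveys. In this study that means using the supplied wireless monitor, with readings passing through the phone to the health record (Sections 6 and 13). The topic is therefore close to the Section 7 hypothesis. It is narrower than the Section 3 objective because it does not mention the pharmacist component. Section 6 gives topics, not questions. The questionnaire and Section 8 are not in the text reviewed, so neither a combined-service item nor a satisfaction item can be called absent.

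**2. Is there an analysis?** The objective is to assess, on a Likert scale, with no test or threshold. Descriptive statistics on post-study ratings are the natural summary. Comfort with the combined service has no true baseline before patients receive it, so a pre/post test would not answer the objective anyway. The t-test sentence follows directly after the bullet on mean blood pressure and control counts, and patient-reported data then get their own sentence. The likeliest reading is that the t-test concerns blood pressure and that satisfaction is a loose label for the post-survey ratings.

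**3. Is satisfaction a stray word?** Section 10 names satisfaction with home telemedicine among the potential benefits. It is a concept the protocol uses, so replacing it in Section 11 could remove an intended analysis.

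**4. What could missing surveys do?** Inputs: N = 20 enrolled (Section 5). *Assumed*: m missing post-surveys, and x comfortable among n = 20 − m completers, with x/n near 80%.

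- Exact 95% limits: lower = the 0.025 quantile of Beta(x, n − x + 1); upper = the 0.975 quantile of Beta(x + 1, n − x).
- Range over all enrolled: x/20 (missing counted as not comfortable) to (x + m)/20 (missing counted as comfortable).
- Width of that range: m/20, or 1/20 = 5 points per missing survey.

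| m | x/n | Proportion | Exact 95% interval | Range over 20 enrolled | Width |
|---|---|---|---|---|---|
| 0 | 16/20 | 80.0% | 56.3% to 94.3% | 80% to 80% | 0 points |
| 2 | 14/18 | 77.8% | 52.4% to 93.6% | 70% to 80% | 10 points |
| 4 | 13/16 | 81.3% | 54.4% to 96.0% | 65% to 85% | 20 points |
| 5 | 12/15 | 80.0% | 51.9% to 95.7% | 60% to 85% | 25 points |
| 6 | 11/14 | 78.6% | 49.2% to 95.3% | 55% to 85% | 30 points |

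With nobody missing, the interval is already 94.3 − 56.3 = 38 points wide. In every row the all-enrolled range lies inside the completers' interval. The two measure different things, since one is sampling error and the other is loss within the sample, so this does not rule out bias. It does show that 20 patients support only a rough figure in every case.

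**5. Does anything depend on the figure?** No. Sections 3 and 11 speak of preliminary data in general. No comfort rate, progression rule or sample-size input is named.

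**The case for a change.** The strongest case for a change is that it costs little and part of it cannot be made later. A few words in Section 11 would settle the terminology, and a question left off the post-survey cannot be asked after patients finish. Comfort is one of only three secondary objectives, and in a sample of 20 each lost response counts.

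Part of this stands. Section 11 does not name comfort, the listed topic is narrower than the objective, and no rule covers a missed post-survey. The claim that there is no matching survey item does not stand, because Section 6 lists one.

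The case for an extra question depends on a questionnaire not seen here. A cut-off for being comfortable and best/worst-case bounds are preferences; the full response distribution meets the objective without either. A remote survey for non-attenders would be convenient, but no loss has been shown that it would prevent. Weekly telehealth contact for six weeks, the gift card at device return, and calls when no reading arrives for 48 hours (Section 12) all work against such loss.

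**Conclusion.** No change to the plan is needed. Followed as written, it collects comfort ratings and describes post-study patient-reported data with descriptive statistics, which is adequate for a descriptive secondary objective in a 20-patient pilot. A sensible analyst would tabulate the post-survey comfort items alongside any satisfaction items and give the number completing out of the number enrolled. That is ordinary reporting, and nothing in Section 11 prevents it or leads to a wrong result.

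The only quantity that follows from the plan's own figures is 5 percentage points of uncertainty per missing survey. The 80% comfort rate and the numbers missing are assumptions, so neither the size nor the direction of any bias can be claimed. The conclusion rests on reading satisfaction as covering the post-survey ratings and the t-test sentence as concerning blood pressure. It would need another look if the questionnaire proved to have no post-study comfort item, or if the comfort figure were made a formal criterion for going on to the larger study.

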12. HUMAN SUBJECT CONSIDERATIONS

The study does not include any vulnerable populations needing added protection beyond the routine. The study population age range (≥ 18 years) will be considered by making sure all study patients understand the study purpose, their role, and our expectations. We will take time to make sure consenting patients want to use telemonitoring and understand how to use the devices. Pharmacists will call patients to answer any questions once they start using the devices, and when they have not monitored their blood pressure in the last 48 hours.

Privacy and confidentiality, based on the Pharmacist Oath, will be maintained always. Informed consent documents will be kept in a locked drawer within a locked office in the Primary Investigator's office for 5 years. After 5 years, these documents will be destroyed through the University shredder. Pharmacists will be conscious to not expose patient information on computer monitors with patient information showing when unattended.

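### Does the 48-hour missed-reading call undermine the three-day clinic-contact rule and bias the comparison of low and high device compliance?

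*Combined protocol and SAP*

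**What the plan says.** Section 6 (Interventions), Devices, has the smartphone set-up that "will be used to monitor blood pressure once a day", with a home monitor for daily use.

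Section 6, Pharmacist Management, gives the patient instruction. It opens with "If any patient has an SBP reading > 160 mmHg or DBP > 100 mmHg", which leads to a recheck after five minutes. If readings "exceed these thresholds for three days in a row, the patients should contact their primary care provider in the clinic for further management". A separate instruction for readings above 180 or 120 mmHg acts on a single reading. The section adds: "There will not be alerts sent to the study pharmacists if the blood pressure readings are above these thresholds".

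The same section sets out what the pharmacists do: "Review results once per week"; a weekly telehealth visit for six weeks in which "the study pharmacists will counsel the patients on their blood pressure readings for that week"; and "Review of evidence-based therapy and recommendations for improvement if needed".

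Section 12 (Human Subject Considerations) says that pharmacists will phone patients to answer questions once they start with the devices, and "when they have not monitored their blood pressure in the last 48 hours".

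Section 11 (Data Management and Analysis) compares mean blood pressure and numbers in control before and after, and plans a chi-square test comparing patients with low and high device compliance. It gives no compliance cut-off and does not clearly state the outcome tested.

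**The concern.** If the three days are calendar days, one day without a reading breaks the run. The call in Section 12 is due only after 48 hours without a reading, so a patient who measures at a fixed hour and skips one day at a time is not called. Such a patient could record only high readings for weeks without meeting the clinic-contact rule or receiving a call, and no alert would reach the pharmacists.

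Two things would be at stake. For the patient, sustained high readings might not lead to the contact the protocol describes. For the analysis, clinic contact can change treatment. If regular measurers are more likely to be directed to the clinic, a difference between compliance groups mixes device use with extra clinic care. The pilot exists to inform a larger study, so a misread compliance effect could carry forward.

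**Working it through.** **Inputs from the documents.** One reading a day; threshold 160 or 100 mmHg; three days running; call after 48 hours without a reading; six weekly visits (6 × 7 = 42 days); total duration eight weeks (8 × 7 = 56 days); 20 patients. The plan states no figure for compliance or for the frequency of high readings, so there is none to reproduce.

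**Assumptions.** p = daily chance of taking a reading (0.9 and 0.5, illustrative); h = share of measured days above the threshold (0.3 to 1); independent days; readings at a fixed hour, so that a call is due only after two missed days; the call always restores a reading the next day.

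**1. Patterns that meet neither rule.** Write 1 for a day with a high reading and 0 for no reading. Of 2^7 = 128 weekly patterns, 81 contain no run of three 1s. Of those, 12 also have no two 0s together, so no call is due. Two days on and one off gives 28 readings in 42 days (38 in 56) with neither rule met; alternate days give 21 (28). The arithmetic is right. It needs successive readings across a skipped day to be no more than 48 hours apart, because a reading taken any later on the second day makes the call due.

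**2. How often such a pattern arises by chance.** With h = 1, I followed the probability of 42 days containing neither three readings in a row nor two missed days in a row. It is 5.1 × 10⁻⁸ at p = 0.5, 1.1 × 10⁻⁷ at p = 0.6, 4.4 × 10⁻⁸ at p = 0.7 and 7.0 × 10⁻¹³ at p = 0.9. The highest is about 1 in 10 million. Only a fixed personal habit would produce it.

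**3. Chance of meeting the three-day rule in 42 days.** Track the current run r of high days. Each day r rises by 1 with probability p × h and otherwise returns to 0. The rule is met at r = 3. After two missed days p is set to 1.

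| h | p = 0.9 | p = 0.5 | p = 0.5, no call |
|---|---|---|---|
| 0.3 | 0.457 | 0.124 | 0.110 |
| 0.5 | 0.920 | 0.431 | 0.389 |
| 0.7 | 0.999 | 0.765 | 0.715 |
| 1 | 1.000 | 0.983 | 0.966 |

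If the call already worked after one missed day, the p = 0.5 values would be 0.144, 0.484, 0.820 and 0.993. The gradient with compliance is therefore real when high readings are intermittent. It nearly disappears when they are sustained.

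**4. Delay under sustained elevation.** Without calls, the expected day of the first three-day run is (1 − p³)/((1 − p)p³):
- p = 0.9: 0.271/(0.1 × 0.729) = 3.7;
- p = 0.5: 0.875/(0.5 × 0.125) = 14.0.

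With the call after two missed days, the p = 0.5 figure falls to 12.3. With a call effective after one missed day it is 10.5.

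**5. The other reading of the rule.** If the three days are successive measured days, the third falls on day 3 with daily readings, day 4 with two on and one off (days 1, 2, 4), and day 5 with alternate days (days 1, 3, 5). The difference is one or two days.

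**6. What the weekly review sees.** In any seven days, two on and one off yields 4 or 5 readings and alternate days yield 3 or 4. Readings go automatically to the record that the pharmacists review weekly and discuss at the visit, and their recommendations carry no run-length condition.

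**7. The sections side by side.** Section 6 tells the patient what to do with high readings. Section 12 tells the pharmacist what to do when readings lapse. Neither refers to the other, and following one never breaches the other.

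**The case for a change.** The strongest case for a change is that patients apply the three-day rule themselves, that the text does not say how a day without a reading counts, and that the call closes little of the gap (0.389 to 0.431 at p = h = 0.5). The weekly review has no written criterion for sending a patient to the clinic, and it may come days after the readings. The remedy would be cheap: a line of definition and a log of calls, contacts and treatment changes, taken at 20 × 6 = 120 existing visits. At an assumed one minute each, that is about two hours.

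Part of this stands. The term is undefined, and the gradient under intermittent elevation is correctly computed. The step to a biased analysis does not stand. Compliance is not randomised, so the comparison is observational whatever the rule says. Clinic contact prompted by home readings is one of the ways monitoring can work, so it lies on the path from device use to blood pressure. Section 11 does not clearly name an outcome for the chi-square test, so no bias can be derived. Compliance groups are not among the objectives in Section 3; whether readings improve is addressed by the before-and-after comparison. A log in 20 patients could describe the mixing but could not adjust for it.

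Section 8 and the patient-facing instructions were not in the text available, so it cannot be said that the definition or a record of contacts is absent.

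**Conclusion.** The concern does not call for a change. The sections are compatible: with the daily readings the plan asks for, the three-day rule operates as written, and the call has a separate purpose. What is left is a small gap in wording, which the investigators can settle when they instruct patients. This review takes no position on how a missed day should count.

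The size depends on the assumptions. The large contrast (92% against 43%) needs intermittent high readings, 50% compliance and the calendar-day reading, and none of these is given in the documents. With sustained high readings it is 100% against 98%, with delay as the main effect. If measured days are meant, the difference is one or two days for the skip-a-day patterns. The instruction for readings above 180 or 120 mmHg is unaffected, and the weekly review shows the remaining readings. Defining the term, keeping a log, and labelling a non-randomised comparison in 20 patients as exploratory would change no planned estimate, test or conclusion.
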